**Table 1 Schedule of Activities during the Induction Phase (cont.)**

- m For atezolizumab, the initial dose will be administered over 60 ( $\pm$  15) minutes. If the first infusion is well-tolerated, subsequent infusions may be administered over 30 ( $\pm$  10) minutes (see Section 6.1.1). The order of infusions should be as per local standard of care. Atezolizumab and carboplatin will be administered on Day 1 of each induction treatment cycle, etoposide will be administered on Day 1, Day 2, and Day 3 of each induction treatment cycle.
- n CT scans (with IV contrast unless contraindicated and oral contrast as appropriate per institutional standards) of the chest, abdomen and pelvis. A CT (with contrast) or MRI scan of the head is required to evaluate CNS metastasis in all participants. Target and non-target lesions must be assigned to allow tumor response assessments per RECIST v1.1. See Section 8.1.1.1 for details.
- o Please see requirements for tumor assessment scans at maintenance screening in [Table 2](#).
- p The optional RBR whole blood sample requires an additional Informed Consent signature. If the optional blood sample for the RBR was not collected on Day 1 of Cycle 1 of the induction phase, it can be collected at any other time during the study after the RBR optional consent has been signed.
- q After informed consent has been obtained but prior to initiation of study treatment, only serious adverse events caused by a protocol-mandated intervention (e.g., invasive procedures such as biopsies, discontinuation of medications) should be reported. After initiation of study treatment, all adverse events must be reported. Please see Section 8.3.1 for the adverse event reporting period.
- r From 7 days prior to enrollment until the treatment discontinuation visit. All such medications must be recorded on the Concomitant Medications eCRF.

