**Table 2 Schedule of Activities during the Maintenance Phase (cont.)**

Events; QLQ-C30 = Quality of Life Questionnaire–Core 30; QLQ-LC13 = Quality of Life Questionnaire–Lung Cancer Module; RBR = Research Biosample Repository; RECIST = Response Evaluation Criteria in Solid Tumors.

- a Maintenance screening can be started as early as all Cycle 4 induction treatment administrations have been completed. The maintenance screening window is up to 28 days. Randomization must occur within 5 weeks (35 days) from the day of the administration of the last dose of induction treatment with atezolizumab, carboplatin, and/or etoposide (whichever occurs last), but Cycle 1, Day 1 of the maintenance phase must not be administered less than 3 weeks (21 days) from Cycle 4, Day 1 of the induction treatment phase. Participants receiving PCI must be randomized within 9 weeks (63 days) from the last dose of induction treatment with atezolizumab, carboplatin, and/or etoposide (whichever occurs last).
- b Assessments should be performed before study treatment infusion unless otherwise noted.
- c Randomized participants will receive their first dose of study treatment the day of randomization into the maintenance phase, if possible. Cycle 1 must be performed within 5 days after randomization. Screening assessments performed  $\leq$  4 days before Cycle 1, Day 1, do not need to be repeated for Cycle 1, Day 1. Day 1 dose administrations are to be performed within a  $\pm$  3-day window, unless treatment is delayed or on hold to manage adverse events. If the scheduled dose administration coincides with a weekend or holiday that precludes administration, administration should be performed as soon as possible but within 7 days following the scheduled D1 dose administration. For Arm A, should one study drug be temporarily interrupted because of toxicity caused by lurbinectedin or atezolizumab, treatment will be restarted such that the administration of both study drugs remains synchronized.
- d The treatment discontinuation visit is to be performed within 30 days of the last study treatment administration or within 30 days from the date the decision was made to permanently discontinue all study treatment.

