#### **9.4.3.5 Incidence and Severity of Adverse Events**

The secondary safety objective will be assessed through summaries of the incidence and severity of adverse events in the SAS.

Verbatim description of adverse events will be mapped to the MedDRA thesaurus terms. Severity for all adverse events will be graded by the investigator according to the NCI CTCAE v5.0. Severity for CRS will also be graded by the investigator according to the American Society of Transplantation and Cellular Therapy (ASTCT) consensus grading scale. All adverse events will be summarized by treatment arm and NCI CTCAE grade. Cytokine release syndrome will also be summarized by treatment arm and the ASTCT consensus grade. All adverse events, serious adverse events, adverse events leading to death, adverse events of special interest, and adverse events leading to study treatment discontinuation that occur on or after the first dose of study treatment (i.e., treatment-emergent adverse events) will be summarized by mapped term, appropriate thesaurus level, and severity grade. For events of varying severity, the highest grade will be used in the summaries. Multiple occurrences of the same event will be counted once at the maximum severity. Deaths and cause of death will be summarized.

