1.1 OBJECTIVES AND ENDPOINTS AND ESTIMANDS

The study will evaluate efficacy, safety, and pharmacokinetics of lurbinectedin when administered in combination with atezolizumab compared with atezolizumab monotherapy in participants with ES-SCLC, who have an ongoing response or stable disease (SD) after completion of 4 cycles of carboplatin, etoposide, and atezolizumab induction treatment. [Table 1](#) presents the primary objectives for the study expressed using the estimands framework in accordance with the International Council for Harmonization (ICH) E9 (R1) statistical principles for clinical trials ([ICH 2020](#)). [Table 2](#) presents the secondary and exploratory objectives and corresponding endpoints.

The term “study treatment” refers to all protocol-mandated treatments and includes atezolizumab in combination with carboplatin and etoposide during the induction phase, and atezolizumab, lurbinectedin, and protocol-mandated prophylactic medications (e.g., granulocyte colony-stimulating factor, anti-emetics) during the maintenance phase.

Most endpoints in [Table 1](#) and [Table 2](#) will be analyzed in randomized participants and therefore, the term “baseline” refers to the time of randomization into the maintenance phase, unless otherwise specified.

Table 1 Primary Objectives and Corresponding Estimands for Randomized Participants

Primary Objective(s)	Estimand Definition

To evaluate the efficacy of lurbinectedin in combination with atezolizumab compared with atezolizumab	
Population: individuals with ES-SCLC who have ongoing complete response (CR), partial response (PR) or SD after completion of 4 cycles of carboplatin, etoposide, and atezolizumab first-line induction treatment, as defined through the inclusion and exclusion criteria for the maintenance phase (see Protocol Section 5.1.2 and 5.2.2, respectively)

Primary Objective(s)	Estimand Definition

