4. STATISTICAL ANALYSES

4.1 GENERAL CONSIDERATIONS

Unless otherwise specified, all efficacy analyses will be performed in the FAS. Participants will be analyzed according to the treatment assigned at randomization by IxRS.

Unless otherwise specified, all safety analyses will be performed in the safety analysis set (SAS). Participants will be analyzed according to the treatment they actually received. Specifically, a participant will be included in the atezolizumab and lorbinecetin combination arm in the safety analyses if the participant receives any amount of lorbinecetin, regardless of the initial treatment assignment at randomization.

Unless otherwise specified, baseline measurements are the last available data obtained prior to the participant receiving the first dose of any component of protocol treatment in the maintenance phase.

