4.3.5 Incidence and Severity of Adverse Events

The secondary safety objective will be assessed through summaries of the incidence and severity of treatment-emergent adverse events (AEs) in the SAS.

Verbatim description of adverse events will be mapped to the Medical Dictionary for Regulatory Activities (MedDRA) thesaurus terms. Severity for all adverse events will be graded by the investigator according to the National Cancer Institute Common Terminology Criteria for Adverse Events (NCI CTCAE) v5.0. Severity for Cytokine release syndrome (CRS) will also be graded by the investigator according to the American Society of Transplantation and Cellular Therapy (ASTCT) consensus grading scale. All adverse events will be summarized by treatment arm and NCI CTCAE grade. Cytokine release syndrome will also be summarized by treatment arm and the ASTCT consensus grade. All adverse events, Grade 3-4 adverse events, serious adverse events, adverse events leading to death, adverse events of special interest, adverse events leading to treatment interruption/modification and adverse events leading to study treatment discontinuation that occur on or after the first dose of study treatment (i.e., treatment-emergent adverse events) will be summarized by preferred term, system organ class, and severity grade. For events of varying severity, the highest grade will be used in the summaries. Multiple occurrences of the same event in the same patient will

be counted once at the maximum severity. Deaths and cause of death will be summarized.

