4.5 OTHER SAFETY ANALYSES

4.5.1 Extent of Exposure

Drug exposure will be summarized during the maintenance phase in the SAS, including duration, dosage, and dose intensity.

Additionally, drug exposure of atezolizumab and chemotherapy during the induction phase will be summarized to include number of doses and dose intensity with use of descriptive statistics for the enrolled SAS.

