4.5.2 Adverse events

AEs, serious AEs, and death (cause of death) during the induction phase will be summarized for the enrolled SAS.

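### As written, SAP 4.3.5 opens the treatment-emergent window in induction, so the by-arm adverse event tables would count pre-randomization events

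*SAP*

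**What the plan says.** SAP 4.3.5 assesses the secondary safety objective in the SAS, by arm and grade, counting a repeated event once per participant at its highest grade. It tabulates adverse events "that occur on or after the first dose of study treatment (i.e., treatment-emergent adverse events) will be summarized by preferred term". Protocol 9.4.3.5 has the same rule: events "that occur on or after the first dose of study treatment (i.e., treatment-emergent adverse events) will be summarized by mapped term".

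The start of the window therefore depends on what study treatment means. SAP 1.1, with the same sentence in Protocol 3, says the term "refers to all protocol-mandated treatments and includes atezolizumab in combination with carboplatin and etoposide during the induction phase", and goes on to include the maintenance drugs.

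Induction events are in the database. Footnote q of the induction schedule (Protocol Table 1) states: "After initiation of study treatment, all adverse events must be reported". Protocol 8.3.1 likewise starts collection with the first treatment.

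Other passages are tied to maintenance:

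- SAP 4.1 takes baseline as the last value before "the first dose of any component of protocol treatment in the maintenance phase".
- SAP 4.5.1: "Drug exposure will be summarized during the maintenance phase in the SAS, including duration, dosage, and dose intensity".
- SAP 4.5.2 gives events, serious events and deaths their own table: those "during the induction phase will be summarized for the enrolled SAS".
- Footnote c of the maintenance schedule (Protocol Table 2): "Randomized participants will receive their first dose of study treatment the day of randomization into the maintenance phase, if possible".

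**The concern.** The safety comparison is meant to show what lurbinectedin adds to atezolizumab in maintenance. Every eligible randomized participant has already had four cycles of carboplatin, etoposide and atezolizumab on study. Protocol Appendix 6 lists myelosuppression, anemia and thrombocytopenia as known effects of both chemotherapy drugs, and nausea and vomiting for etoposide. The same appendix lists these toxicities for lurbinectedin. The events that the comparison most needs to separate are thus ones that induction also produces, with equal expectation in the two arms.

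If induction events enter the tables, both arms rise by a common background and the contrast shrinks. Because each event is kept at its highest grade, a worse induction grade can also hide the grade reached in maintenance.

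**Working it through.** **Reading the rule.** The documents give no figure for this window, so there is none to reproduce. The first step is whether any text closes the window to induction.

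1. SAP 4.3.5 uses the defined term without a phase limit.
2. The SAS definition (SAP 3) limits who is counted. It sets no limit on event dates.
3. SAP 4.1 and 4.5.1 name the maintenance phase explicitly, so the authors wrote that limit where they applied it. SAP 4.3.5 does not have it.
4. SAP 4.5.2 adds an induction summary in a different population. It does not remove those events from the SAS tables.
5. Local usage does not settle the term. Footnote c of Table 2 uses the first dose of study treatment for maintenance Cycle 1, while footnote b of Table 1 uses the same phrase for induction Cycle 1.
6. The protocol has the same wording as the SAP, and SAP 5 says there is no additional supporting document.

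Read literally, the window opens at induction Cycle 1, Day 1.

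**Length of the added window.** Four 21-day cycles put Cycle 4, Day 1 at 3 × 21 = 63 days after the start. Maintenance dosing may not begin within 21 days of that date, so the added period is at least 63 + 21 = 84 days on the nominal schedule. For scale, the planning median PFS in the control arm is 2.6 months (SAP 2.2.3), and 2.6 × 30.44 ≈ 79 days.

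**Effect on one event term.** Let I be the event in induction, with probability p in both arms (expected under randomization), and M the event in maintenance.

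- Tabulated incidence in arm k = p + (1 − p) × P(M | no I, arm k).
- Tabulated risk difference = (1 − p) × [P(M | no I, A) − P(M | no I, B)]. No independence is assumed.
- Equivalently, it is the true maintenance risk difference minus p times the risk difference among those who had the event in induction. It shrinks whenever Arm A's excess is also present in that group.

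If I and M are also independent, the true risk difference is multiplied by (1 − p): 0.9, 0.8, 0.6 or 0.4 for p = 10%, 20%, 40% or 60%.

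Illustration with assumed maintenance incidences of 40% (A) and 20% (B), under independence, where tabulated incidence = 1 − (1 − p)(1 − maintenance incidence):

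| Assumed p | Arm A | Arm B | Difference | Ratio |
|---|---|---|---|---|
| 0 (maintenance window) | 40% | 20% | 20 points | 2.00 |
| 30% | 58% | 44% | 14 points | 1.32 |
| 50% | 70% | 60% | 10 points | 1.17 |
| 70% | 82% | 76% | 6 points | 1.08 |

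None of these rates comes from the trial documents, and no particular p is claimed.

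**Where p is near zero.** Protocol 4.1 and 5.1.2 exclude anyone with fewer than four induction cycles. An event that ended induction early therefore keeps the participant out of the SAS, and events leading to treatment discontinuation should be diluted little or not at all.

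**The case against.** The strongest reply is that context already settles the matter. Safety is split by phase throughout: baseline, SAS exposure, patient-reported summaries and the separate induction table. Footnote c of Table 2 uses the key phrase for maintenance in exactly the population that forms the SAS. The SAS definition itself requires a dose of atezolizumab or lurbinectedin. Since every eligible randomized participant has already received atezolizumab in induction, that condition has meaning only as a maintenance dose. This makes a maintenance-only intent likely, and it stands as evidence of intent. It does not exclude any event, because the rule in SAP 4.3.5 rests on a formally defined term that includes induction.

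The reply is also right on size: p is assumed, and eligibility selection protects some categories.

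A reader might infer three stronger points that the documents do not support.

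- *That Arm B events leading to dose modification could come only from induction.* SAP 4.3.5 plans one combined interruption/modification category, and atezolizumab may be interrupted in maintenance, so Arm B contributes events to it under either window.
- *That the current text loses an induction-onset event that turns fatal in maintenance.* The literal window would count it. Only a window based on onset alone would drop it, which is a caution about the remedy.
- *That the tables have been built on the wrong window.* Nothing shows which window was programmed.

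**Conclusion.** The point holds as a defect in a stated rule. SAP 4.3.5 and Protocol 9.4.3.5, applied with their own definition of study treatment, place pre-randomization induction events in the by-arm tables for the secondary safety objective. Risk differences for most non-fatal events would be pulled toward zero.

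The (1 − p) factor rests on equal induction incidence in the two arms. Applying it to the true maintenance difference also needs independence of induction and maintenance risk. The actual size is unknown, because the documents give no induction event rates by term.

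The tables are descriptive, so no formal test is affected, and a maintenance-only window was probably meant. The correction is worth making because it is short and the tables carry the trial's safety comparison. It is not evidence that reported results are wrong.

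**What to change.** In SAP 4.3.5, define treatment-emergent events for the SAS as those with onset, or with documented worsening in grade, in seriousness or to a fatal outcome, on or after the first maintenance-phase dose of study treatment. Keep induction events in the enrolled-SAS summary of SAP 4.5.2. Including worsening and fatal outcome avoids losing events that began in induction and became important later.

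The Version 8 rationale in the protocol says that the final overall survival cutoff has been reached and that some analyses are complete. If the tables already exist, state the window used and re-run them only if it opened in induction.

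The cost is a short definition and minor programming. The downside is that some ongoing events with undated worsening may be missed. Protocol A3-7.4 asks for the initial and most extreme grades, but for a date only when an event becomes serious, and Protocol 5.1.2 lets some low-grade events continue into maintenance. Counting every undated worsening as treatment-emergent is not a good remedy, because it would bring induction events back into the tables.

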4.3.6 Time to Confirmed Deterioration

Confirmed clinically meaningful deterioration for physical functioning and Global Health Status (GHS)/Quality of Life (QoL) is defined as a clinically meaningful decrease from baseline in the physical functioning or GHS/QoL scores that must be held for at least two consecutive assessments or an initial clinically meaningful decrease above baseline followed by death attributable to cancer progression within 6 weeks of the last deteriorated PRO assessment. A score change of \geq 10-point change in GHS/QoL and functional subscale scores is perceived by participants as clinically meaningful (Osoba et al. 1998).

For time to confirmed deterioration (TTCD), data for participants will be censored at the last time when they completed an assessment if they have not experienced a confirmed clinically meaningful deterioration at the clinical cutoff date. If no baseline or post-baseline assessment is performed, participants will be censored at the randomization date. According to the while-on-treatment/while-alive strategy, participants who die before reporting any clinically meaningful deterioration will be censored at the last time they completed an assessment. Time to confirmed deterioration using the European Organization for Research and Treatment of Cancer (EORTC) scale will be analyzed with use of the same methods as for PFS.

[REDACTED]

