- ✗ PRO questionnaires (EORTC QLQ-LC13, EORTC QLQ-C30, EORTC IL46, and EQ-5D-5L) will be completed by the participants at the start of the clinic visit before discussion of the participant's health state, laboratory results, or health record; before administration of study treatment; and/or prior to the performance of any other study assessments that could bias the participant's responses. In scenarios where laboratory assessments (e.g., blood draws) are done in a different clinic than the one providing treatment or when they are done on a different day than study treatment administration, laboratory assessments can be completed before the completion of PROs as long as results have not been discussed with the participant. If the participant comes to the clinic for study drug administration, completes the PRO questionnaires and then does not receive study treatment (i.e., a decision is made that study treatment cannot be administered on that day due to the participant's health status), the collected PROs should be kept and questionnaires for this timepoint should not be re-administered on the day of the delayed study drug administration. The questionnaires will be completed on Cycle 1, Day 1 (baseline); Cycle 2, Day 1; Cycle 3, Day 1; Cycle 4, Day 1, and Cycle 5, Day 1. From Cycle 6 onwards, the questionnaires will be completed at every other study treatment cycle prior to the administration of study drug (i.e., on Cycle 6, Day 1; Cycle 8, Day 1; Cycle 10, Day 1; etc.). PROs will be collected during the treatment period and at the study treatment discontinuation visit. During follow-up, PROs (EORTC QLQ-C30, EORTC QLQ-LC13 and EQ-5D-5L) will be completed at 3 months ( $\pm$  30 days) and 6 months ( $\pm$  30 days). The PRO instruments will be self-administered by the participant via ePRO device or may be collected remotely on non-visiting dates (e.g., during follow-up or in exceptional circumstances).

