#### **9.4.3.6 Time to Confirmed Deterioration**

Time to confirmed deterioration (TTCD) for physical functioning and global health status (GHS)/QoL using the EORTC QLQ-C30 is defined as the time from the date of randomization until the first confirmed clinically meaningful deterioration.

Confirmed clinically meaningful deterioration for physical functioning and GHS/QoL is defined as a clinically meaningful decrease from baseline in physical functioning or GHS score that must be held for at least two consecutive assessments or an initial clinically meaningful decrease above baseline followed by death.

A score change of  $\geq 10$ -point change in GHS/QoL and functional subscale score is perceived by participants as clinically meaningful (Osoba et al. 1998).

For TTCD, data for participants will be censored at the last time when they completed an assessment if they have not experienced a confirmed clinically meaningful deterioration at the clinical cutoff date. If no baseline or post-baseline assessment is performed, participants will be censored at the randomization date. Time to confirmed deterioration using the EORTC scale will be analyzed with use of the same methods as for PFS. Further details regarding the TTCD analysis for the EORTC measures will be described in the Statistical Analysis Plan.

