1. INTRODUCTION

The Statistical Analysis Plan (SAP) provides details of the planned analyses and statistical methods for Study GO43104 (IMforte), a Phase III, randomized, open-label, multicenter study of lurbinectedin in combination with atezolizumab compared with atezolizumab as maintenance therapy in participants with extensive-stage small-cell lung cancer (ES-SCLC) following first-line induction therapy with carboplatin, etoposide and atezolizumab. The background of the study can be found in the study protocol.

The analyses described in this SAP will supersede those specified in Protocol GO43104 for the purposes of a regulatory filing.

There are no changes to the planned analyses described in the protocol.

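### SAP 4.3.6 narrows the death part of the time-to-confirmed-deterioration event, so SAP Section 1 is wrong to say that nothing changed from the protocol

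*SAP*

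**What the plan says.** Both documents count a TTCD event when a drop of at least 10 points in QLQ-C30 physical functioning or global health status is held for two consecutive assessments. Both add a second route for participants who die before a drop can be confirmed, and here they differ.

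- Protocol 9.4.3.6 accepts "an initial clinically meaningful decrease above baseline followed by death". It gives no limit on cause or timing. (Both documents write above where a decrease from baseline must be meant.)
- SAP 4.3.6 accepts an initial drop only if it is "followed by death attributable to cancer progression within 6 weeks of the last deteriorated PRO assessment".

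Three other statements bear on the difference:

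- Protocol 9.4.3.6: "Further details regarding the TTCD analysis for the EORTC measures will be described in the Statistical Analysis Plan".
- SAP Section 1: "The analyses described in this SAP will supersede those specified in Protocol GO43104 for the purposes of a regulatory filing".
- SAP Section 1, immediately afterwards: "There are no changes to the planned analyses described in the protocol".

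SAP 4.3.6 also has a while-alive rule, under which "participants who die before reporting any clinically meaningful deterioration will be censored at the last time they completed an assessment".

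**The concern.** The SAP adds two restrictions to the event definition, one on cause of death and one on its timing. Together they turn some protocol events into censored observations. A reader who relies on SAP Section 1 will take the reported TTCD to follow the protocol definition, which it does not.

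The cause restriction needs particular care. The trial is open-label, and Appendix 3 (A3-7.8) has the investigator attribute deaths to SCLC progression. Protocol 4.2 expects the arms to differ in toxicity. A non-progression death after an unconfirmed drop in quality of life is an event under the protocol and is censored under the SAP, so reclassification need not be balanced between arms.

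SAP 2.2.1 controls type I error for OS and IRF-assessed PFS only. What is at stake is therefore the reading of the quality-of-life result, not the primary conclusions.

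**Working it through.** The documents give no TTCD sample size, event count or power, so there is no stated figure to reproduce. The check has three steps.

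**1. The two definitions, case by case**

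| Participant's course | Protocol 9.4.3.6 | SAP 4.3.6 |
|---|---|---|
| Two consecutive deteriorated assessments | Event | Event |
| One drop, then progression death within 6 weeks | Event | Event |
| One drop, then progression death after 6 weeks, no confirming assessment | Event | Censored at last assessment |
| One drop, then death from another cause at any time, no confirming assessment | Event | Censored at last assessment |
| Death with no earlier drop | Censored | Censored |

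Rows three and four differ. The while-alive rule covers only the last row, where the documents agree, so it does not explain the difference.

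**2. Whether the 6-week limit has effect when no questionnaire is missed**

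Inputs are from Protocol Table 2. Questionnaires are completed every 21-day cycle to Cycle 5, and every other cycle from Cycle 6. The follow-up period starts at the discontinuation visit. "During follow-up, PROs (EORTC QLQ-C30, EORTC QLQ-LC13 and EQ-5D-5L) will be completed at 3 months" and again at 6 months, each ±30 days. None is scheduled later.

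- On treatment: the longest planned gap is 2 × 21 = 42 days, which equals the 6-week window. Apart from visit windows and dose delays, a death before the next questionnaire falls inside it.
- Discontinuation visit to 3 months: about 91 days (61 to 121). Beyond the window: 91 − 42 = 49 days (19 to 79).
- 3 to 6 months: 183 − 91 = 92 days (153 − 121 = 32, to 213 − 61 = 152). Beyond the window: 92 − 42 = 50 days (0 to 110).
- After the 6-month questionnaire: open-ended. A first drop there cannot be confirmed by a second scheduled assessment, so death is the only route to an event.

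**3. Illustration for a first drop at the 6-month questionnaire**

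The following are assumptions, not figures from the documents: exponential survival from that date with median m months, and F months of later follow-up. The upper value of m, 12.5 months, borrows the control-arm median OS from randomization in SAP 2.2.2.

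The probability of death by t months is P(t) = 1 − 2^(−t/m). Six weeks is 42/30.4375 = 1.38 months. The share of deaths by F that fall after 6 weeks is 1 − P(1.38)/P(F).

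For m = 3 and F = 6: P(1.38) = 0.273, P(6) = 0.750, share = 1 − 0.273/0.750 = 0.64.

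| Median m (months) | P(6 weeks) | F = 6 | F = 12 | F = 24 |
|---|---|---|---|---|
| 3 | 0.273 | 0.64 | 0.71 | 0.73 |
| 6 | 0.147 | 0.71 | 0.80 | 0.84 |
| 9 | 0.101 | 0.73 | 0.83 | 0.88 |
| 12.5 | 0.074 | 0.74 | 0.85 | 0.90 |

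These later deaths would be censored under the SAP whatever their cause. The cause restriction then also removes non-progression deaths inside the window.

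**The case against.** The strongest reply is that the documents already settle the matter. The protocol leaves TTCD detail to the SAP, the SAP supersedes the protocol for filing, and SAP 4.3.6 prints its rule in full, so nobody need be in doubt about which definition applies. The protocol's lack of a time limit is also partly silence. Read literally, it lets a much later death confirm a drop from which the participant had recovered, and setting a window is the kind of detail a SAP supplies. The 6-week window fits the on-treatment schedule. The 64% to 90% range describes a selected group, probably small: people event-free through treatment, discontinuation and the 3-month form, and still completing questionnaires at 6 months.

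Much of this stands. The governing rule is identifiable, the window is reasonable on treatment, and the timing problem with complete questionnaires is essentially a post-discontinuation one. The percentages are not an effect on TTCD, and part of their size comes from comparing a finite window with an unlimited one.

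It does not rescue the statement in SAP Section 1. The protocol defers further details of the analysis but states the event definition itself, and a restriction on cause of death is hard to call detail. Supersession determines which rule governs; it does not make a changed rule unchanged.

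One caveat remains. The public SAP lacks its title page, so the protocol version it was written against is not visible. The readable change summaries for protocol Versions 7 and 8 mention no TTCD change, though some items are redacted. Version 8 still carries the unrestricted rule.

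**Conclusion.** The concern holds. The SAP changes which participants count as TTCD events, and its Section 1 statement is wrong for this endpoint. That conclusion comes from the wording alone and needs no assumption.

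The size of the effect on the TTCD result cannot be derived from the documents: neither the number of participants reclassified nor the direction between arms is known. The scheduled time outside the 6-week window is about 49 days after the discontinuation visit, about 50 days between the two follow-up questionnaires, and open-ended after the second. The 64% to 90% range is a share of deaths in one situation under the stated assumptions, not a participant count. The point should be corrected, but it does not touch the OS or PFS analyses.

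**What to change.** 1. In SAP Section 1, replace the no-changes statement with an entry listing the TTCD death rule as a change from protocol 9.4.3.6, with its reason. If the SAP can no longer be amended, put the entry in the clinical study report's list of changes.
2. Keep the SAP rule as the main TTCD analysis.
3. Report TTCD under the protocol rule (death from any cause, no time limit) as a labelled sensitivity analysis. Give the number of participants reclassified per arm, split into death from another cause and death later than 6 weeks.

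The cost is one paragraph and a little programming. No new data are needed: date and cause of death are already collected. No further questionnaire data can be added, because collection stops with protocol Version 8. The drawback is that the protocol rule can let a late death confirm a recovered drop, so it serves only as a comparison. The Version 8 rationale says the final OS cut-off has been reached and some analyses are complete; if TTCD is among them, the sensitivity analysis must be labelled post hoc.
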